6.17.1.4 Serious Adverse Events

Serious adverse events (SAEs) are described in [Section 6.4.5 of Protocol 812P303](#). A listing of SAEs and AEs leading to discontinuation will be presented. All subject deaths during this study will be collected and presented in a listing. The information presented will include date of death, days on study, cause of death, and relationship of death to study drug

Adverse event data will be presented in Listings 16.2.7.1, 16.2.7.2, and 16.2.7.3.

6.17.2 Laboratory Data

The change from baseline will be calculated as post-baseline value minus baseline value.

For each laboratory parameter, the following will be displayed for baseline and Week 8 (EOS).

- Summary statistics (n, mean, SD, median, minimum, and maximum) by treatment group for the actual and change from baseline values will be presented in Tables 14.3.2.1.1 and 14.3.2.2.1.
- Laboratory values will be flagged as abnormally low (L) if the value $<$ lower limit of the normal range, normal (N) if the value is within normal range or abnormally high (H) if the value $>$ upper limit of the normal range. Shift tables for the change from baseline to endpoint Week 8 (EOS) will be presented in Tables 14.3.2.1.2 and 14.3.2.2.2. Laboratory data will be presented in Listings 16.2.8.1 and 16.2.8.2.

6.17.3 Vital Signs

Vital signs parameters include: heart rate, diastolic and systolic blood pressure, respiratory rate, and temperature.

The change from baseline will be calculated as post-baseline value – baseline value.

Table 3: Vital Signs Normal ranges

Parameter, unit	Normal range	
	Lower limit	Upper limit
Pulse, bpm	70	120
DBP, mmHg	50	80
SBP, mmHg	90	120
Temperature, °C	35.5	37.5
Respiratory rate, bpm	18	25

Source: <http://www.pedscases.com/pediatric-vital-signs-reference-chart>

Values equal to the boundaries are still considered normal (N).

A value is classified as abnormally low (L) when the value < lower limit of the normal range.

A value is classified as abnormally high (H) when the value > upper limit of the normal range.

Vital signs will be summarized by treatment group using descriptive statistics (for quantitative parameters) in Table 14.3.3.1 and frequency tables (categorical variables) in Table 14.3.3.2.

Subject Listing of Vital Signs will be presented in Listings 16.2.9.1 and 16.2.9.2.

16.17.4 Twelve (12)-Lead ECG

ECG parameters include HR, QRS, PR, and QTc.

If there is no original QTc in the database, then the QTc will be calculated using the following formulae:

$$\text{Fridericia's cube-root corrected QT : QTcF (ms)} = \text{QT (ms)} \times \sqrt[3]{\frac{\text{HR(bpm)}}{60}}$$

Table 4: Normal ECG ranges

Parameter, unit	Normal range	
	Lower limit	Upper limit
HR, bpm	60	140

PR, ms	90	170
QRS, ms	40	90

Source: <http://learn.pediatrics.ubc.ca/body-systems/cardiology/approach-to-pediatric-ecg/>

Values within boundaries and equal to the boundaries are still considered normal (N).

A value is classified as abnormally low (L) when the value < lower limit of the normal range.

A value is classified as abnormally high (H) when the value > upper limit of the normal range.

For the QT and QTc parameters, the following categorizations will be done:

- of the actual values: ≤ 450 ms, 450 ms < to ≤ 480 ms, 480 < to ≤ 500 ms, >500 ms
- of the changes from baseline: ≤ 30 ms (including all decreases in QT), $30 < to \leq 60$ ms, >60 ms.

ECG parameters will be summarized by treatment group using descriptive statistics (for quantitative ECG parameters) in Table 14.3.4.1 and frequency tables (for categorical parameters) in Table 14.3.4.2, Table 14.3.4.3, and Table 14.3.4.4.

Subject Listing of ECG: Parameters for actual and derived variables will be presented Listings 16.2.10.1 and 16.2.10.2.

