3.5 Sample Size and Power Considerations

Seventy-two subjects per treatment group in the ITT population will yield 90% power at a significance level of 0.05 (two-sided) using a two-sample t-test with equal allocation to the treatment

groups. This assumes an effect size of 0.547, observed in the comparison of SPN-812 200 mg and placebo in the SPN-812 Phase IIb study (based on the CFB to endpoint in the ADHD-RS-IV total score). A total of 300 subjects (100 subjects in each of the three treatment groups) will be randomized to account for an anticipated 27.9% of randomized subjects not completing the study.

4 Definitions and Derivations

1. Baseline: Unless specified otherwise, baseline is defined as the non-missing value collected most recent to and before the time of the very first dose of the SM.
2. The study day (DY) is calculated as Visit date minus Reference date + 1 day if the visit date occurs on or after the reference date or Visit date minus Reference date if the visit date occurs before the Reference date, where the Reference date is defined as the first dose date (DY=1)
3. The change from baseline at a given Visit = observed value at that Visit minus observed value at baseline
4. ADHD-RS-5 total score =sum of scores for the 18 behaviors
5. ADHD-RS-5 Inattention subscale score = sum of scores for the first 9 behaviors
6. ADHD-RS-5 Hyperactivity/Impulsivity Subscale score = sum of scores for the last 9 behaviors
7. Conners 3-Parent Reported score: Composite T-score calculated by averaging over the 6 domains
8. Conners 3-Parent Reported score: T-score for individual domain: inattention, hyperactivity/impulsivity, aggression, executive functioning, learning problems, and relationships
9. Conners 3-Self Reported score domains: Composite T-score over the 5 domains
10. Conners 3-Self Reported score domains: inattention, hyperactivity/impulsivity, aggression, learning problems, and relationships
11. WFIRS-P score=average of all 50 items
12. WFIRS-P subscale scores: average of items of following 6 subdomains: Family, School (learning and behavior), Life Skills, Child's Self-Concept, Social Activities, and Risky Activities
13. PSI-4-SF: score=sum of all 36 items
14. PSI-4-SF: subscale scores: sum of items of following 3 subdomains: parental distress (PD), parent-child dysfunctional interaction (P-CDI), and difficult child (DC)

5 Study Variables

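### The SAP takes QTc from the database under an unnamed correction formula and uses Fridericia only as a fallback, so QTc values and changes need not share one formula

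*SAP*

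**What the plan says.** SAP Section 16.17.4 (6.17.4 in the table of contents) treats QTc as one variable: "ECG parameters include HR, QRS, PR, and QTc". Its source rule is "If there is no original QTc in the database, then the QTc will be calculated", followed by Fridericia's cube-root correction and no other formula. Nothing says which correction a QTc already in the database carries.

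The section then sets category limits: "For the QT and QTc parameters, the following categorizations will be done". Absolute values are cut at 450, 480 and 500 ms, and changes from baseline at 30 and 60 ms, with all decreases placed in the lowest change category. The results go into descriptive and frequency tables by treatment group (Tables 14.3.4.1 to 14.3.4.4). The section does not provide for separating QTcF from a QTc obtained another way.

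Two other places bear on the point:

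- Table 1 in Section 3.2 schedules the 12-lead ECG at Screening and at End of Study only.
- Section 4 says "baseline is defined as the non-missing value collected most recent to and before the time of the very first dose of the SM". It does not require the baseline and post-baseline values to use the same correction.

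**The concern.** QTc correction formulas agree at 60 bpm and move apart as heart rate rises. The SAP's own normal ECG heart-rate range for these children is 60 to 140 bpm (Table 4), so most normal records lie where the formulas can differ. If the two ECGs behind a change score were corrected differently, the change contains the difference between formulas as well as any change in the child.

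Each subject normally contributes one Screening-to-End-of-Study pair, so a mismatch is not averaged over visits. A Fridericia baseline followed by a Bazett value would look like prolongation. The reverse order would hide a real increase, because a reduced or negative change falls in the lowest category. The absolute categories are exposed too, since one tracing can fall on either side of 450 ms depending on the formula.

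**Working it through.** The SAP gives no figure on this point to reproduce. The check has five parts.

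**1. The printed formula.** QTcF = QT × (HR/60)^(1/3). With RR = 60/HR in seconds this equals QT / RR^(1/3). At QT 350 ms and HR 90 both forms give 400.6 ms. The formula is correct.

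**2. Gap on an identical ECG if the reported value is Bazett.** Bazett is an assumption, as is the QTcF range of 360 to 440 ms. The SAP states neither.

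QTcB = QT × (HR/60)^(1/2), so QTcB − QTcF = QTcF × [(HR/60)^(1/6) − 1].

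| HR (bpm) | QTcF 360 ms | QTcF 400 ms | QTcF 440 ms |
|---|---|---|---|
| 70 | 9.4 | 10.4 | 11.5 |
| 80 | 17.7 | 19.6 | 21.6 |
| 90 | 25.2 | 28.0 | 30.8 |
| 100 | 32.0 | 35.5 | 39.1 |
| 120 | 44.1 | 49.0 | 53.9 |
| 140 | 54.6 | 60.7 | 66.7 |

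**3. Heart rate at which the gap alone reaches a category limit.** For a gap of d ms, HR = 60 × (1 + d/QTcF)^6. For QTcB to reach 450 ms, HR = 60 × (450/QTcF)^6.

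| QTcF (ms) | Gap 30 ms | Gap 60 ms | QTcB at 450 ms |
|---|---|---|---|
| 360 | 97.0 | 151.3 | 228.9 |
| 380 | 94.7 | 144.6 | 165.5 |
| 400 | 92.6 | 138.8 | 121.6 |
| 420 | 90.8 | 133.7 | 90.8 |
| 440 | 89.1 | 129.2 | 68.7 |

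The 30 ms limit is reached inside 60 to 140 bpm for every QTcF shown. The 450 ms limit is reached inside that range for QTcF 400 to 440 ms. The 60 ms limit is reached at 129 to 139 bpm for QTcF 440 to 400 ms, and not within the range for 360 or 380 ms.

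One tracing as illustration: QT 350 ms at HR 100 gives QTcB = 350 × 1.6667^(1/2) = 452 ms and QTcF = 350 × 1.6667^(1/3) = 415 ms. The gap is 37 ms, across the 450 ms line.

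**4. Effect on a change score.** With Fridericia at Screening and Bazett at End of Study, the recorded change is the true QTcF change plus the End of Study gap. In the reverse order it is the true change minus the Screening gap. For example, take a true rise of 35 ms from a Screening ECG with QTcF 400 ms at HR 80. If Screening was reported as Bazett and End of Study calculated as Fridericia, the recorded change is 35 − 19.6 = 15.4 ms, in the lowest category.

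**5. Other possible formulas, at QTcF 400 ms.** Framingham is QT + 154 × (1 − RR). Hodges is QT + 1.75 × (HR − 60).

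| HR (bpm) | Framingham − Fridericia | Hodges − Fridericia |
|---|---|---|
| 70 | 2.0 | −2.5 |
| 80 | 1.9 | −1.6 |
| 90 | 0.8 | 1.9 |
| 100 | −1.0 | 7.4 |
| 120 | −5.5 | 22.5 |
| 140 | −10.4 | 41.6 |

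If every reported value is Fridericia, the gap is 0 ms at all heart rates.

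**The case against.** The strongest reply is that the fallback sentence can be read for the database as a whole: if no QTc was captured, calculate QTcF throughout. The fallback then mixes nothing. This reading is fair, and the wording does not exclude it. It does not settle which formula reported values carry, or whether they all carry the same one.

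Second, the size rests on Bazett. That is right. With Framingham, 30 ms is not approached; with Hodges, it is passed only between 120 and 140 bpm. The SAP does not let a reader know which case applies.

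Third, how ECGs are read and corrected may be set in the protocol or an ECG procedure. A reader might infer that sites in this trial do use different formulas. Nothing in the SAP shows that; it only fails to exclude it.

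Fourth, mixing through the fallback needs exactly one of a subject's two ECGs to lack a QTc, and no frequency can be derived. The tables are descriptive, and under randomisation mixing would mainly add noise to all arms alike. This stands as a limit on between-arm bias, unless missing QTc or heart rate differs by arm. It does not protect individual classifications or category counts.

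Fifth, the SAP does not say that QT and HR exist for every ECG. QT is absent from its list of ECG parameters and appears only in the formula and the categorisation. The remedy therefore has to be conditional on both being recorded.

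**Conclusion.** The concern holds in a limited form. The rule permits QTc values, and the one change score a subject normally has, to rest on different correction formulas. On the database-wide reading, it still leaves the formula unnamed and not required to be uniform. Nothing else in the SAP resolves this.

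If reported values are Bazett, the realistic exposure is at the 30 ms change limit (from about 89 to 97 bpm for QTcF 440 to 360 ms) and the 450 ms absolute limit. The exposure is smaller under Hodges, about 10 ms or less under Framingham (both at QTcF 400 ms, HR 70 to 140), and nil under Fridericia.

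A reader might infer that formula mixing can produce false shifts at every safety threshold. The document does not support that. It calls these limits categorisations and attaches no alert or action to them, and even under Bazett the 60 ms limit is met only near or above the top of the normal heart-rate range. Nor does the SAP show that mixing will occur. The point concerns a descriptive safety display and leaves the efficacy conclusions untouched.

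**What to change.** Replace the source rule in Section 16.17.4. Calculate QTcF from QT and HR with the formula already printed for every ECG where both are recorded. Base all QTc summaries, absolute categories and change categories on that variable, label it QTcF in Tables 14.3.4.1 to 14.3.4.4, and show any reported QTc only in the listings, with its formula if known. This brings the formula-mixing artefact to 0 ms at every heart rate.

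The cost is about a sentence of SAP wording plus the derivation. The downside is that a record lacking QT or HR would have missing QTcF in the tables even if a QTc was reported. Section 6.6.2 does not impute such safety data, so the number of these records should be shown.

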16.17.5 Physical examinations

All physical examination findings will be presented in Listing 16.2.11.1.

Actual values and changes from baseline will be calculated at EOS for weight, height and BMI and presented in Listing 16.2.11.2.

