3.2 Schedule of Visits and Procedures Study

All subjects who are randomized and take any SM will be followed according to the protocol regardless of the number of doses of SM taken, unless consent for follow-up is withdrawn. [Table 1](#) below presents the Schedule of Visits and Procedures for the study.

Table 1: Schedule of Visits and Procedure

Period	Screening	Treatment Phase			
		Titration		Maintenance	
		Baseline, Randomization			End of Study ⁱ
Visit Number	1	2	3, 4	5-9	10
Visit Day		1	7, 14	21, 28, 35, 42, 49	56
Visit Window (days)	≤28d before V2		±2	±2	±2
Informed Consent/Accent (if applicable) ^a	X				
Medical and Psychiatric History	X				
Mini-KID	X				
Demographics	X				
Urine Drug Screen	X				
Randomization		X			
Physical Exam ^b	X				X ^c
Inclusion/Exclusion Criteria	X	X			
ECG (12-lead)	X				X
Vital Signs ^d	X	X	X	X	X
Hematology	X				X
Serum Chemistry	X				X

Pharmacogenomic sample	X				
Urine Pregnancy test, FOCP only		X			X
CGI-S	X	X			
CGI-I			X	X	X
C-SSRS	X	X	X	X	X
ADHD-RS-5	X	X	X	X	X
WFIRS-P, PSI-4-SF		X			X
Conners 3 ^e – parent, self		X			X
Concomitant Medication	X	X	X	X	X
Adverse Events		X ^f	X	X	X ^f
Drug Dispensed		X ^g	X	X	
Drug Return, Compliance			X	X	X
Optional PK Blood Sampling ^h			X	X	X

a To be obtained prior to performing any study procedures.

b Includes height and weight, excludes genitourinary system

c Changes from Screening only

d Seated (5 min) heart rate and blood pressure, temperature, respiratory rate

e Self report = 8-11 year olds only

f At Baseline, AEs are recorded only after SM is administered. Subjects with serious adverse events at EOS will be followed until the event has resolved or considered stable.

g Titration will begin after first dose of SM is administered

- ^h An optional PK substudy will take place between Visits 3 and 10, inclusive. Samples will be taken pre-dose and post-dose at Hours 1, 2, 4, and 6.
- ⁱ EOS or last visit in the case of early discontinuation.

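### Measured change in weight, height and BMI goes only to a subject listing; no planned output compares it between treatment arms in growing children

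*SAP*

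**What the plan says.** Height and weight belong to the physical examination. Footnote b to Table 1 (SAP section 3.2) describes that examination: "Includes height and weight, excludes genitourinary system". Table 1 schedules it at Screening (Visit 1) and end of study (Visit 10) only.

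Section 16.17.5 (listed as 6.17.5 in the table of contents) fixes two outputs, both listings. The first: "All physical examination findings will be presented in Listing 16.2.11.1". The second: "Actual values and changes from baseline will be calculated at EOS for weight, height and BMI and presented in Listing 16.2.11.2".

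The neighbouring safety sections also plan tables:

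- Laboratory data (6.17.2): summary statistics "by treatment group for the actual and change from baseline values will be presented in Tables 14.3.2.1.1 and 14.3.2.2.1".
- Vital signs (6.17.3): "Vital signs will be summarized by treatment group using descriptive statistics (for quantitative parameters) in Table 14.3.3.1".
- ECG (16.17.4): "ECG parameters will be summarized by treatment group using descriptive statistics (for quantitative ECG parameters) in Table 14.3.4.1".
- C-SSRS (16.17.6): counts and percentages by treatment group in Table 14.3.5.

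The vital-signs tables do not pick up body size, because section 6.17.3 defines their content: "Vital signs parameters include: heart rate, diastolic and systolic blood pressure, respiratory rate, and temperature". Section 6.7 tabulates height, weight and BMI as baseline characteristics of the ITT population (Table 14.1.2.1), with no follow-up values.

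**The concern.** One of the trial's stated aims (section 2.2.4) is safety and tolerability in children with ADHD. Children of this age gain weight and height over a few months without any treatment, so a change from baseline has no natural zero. A child whose weight gain slowed on treatment can show a listed change near zero, which reads as no effect. A listing sorted by subject identifier does not bring the arms together, so a modest average shortfall in one arm would be hard to see.

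The randomized placebo arm shows what growth alone would have produced over the same interval. If the plan is followed exactly, no output uses it for measured weight, height or BMI. The SAP derives each child's change and then stops short of the comparison that would make it interpretable.

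**Working it through.** **1. Is there a by-arm summary of change elsewhere in the SAP?**

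| Measure | Section | Change from baseline derived | By-arm table after baseline |
|---|---|---|---|
| Laboratory values | 6.17.2 | yes | 14.3.2.1.1 and 14.3.2.2.1, plus shift tables |
| Vital signs | 6.17.3 | yes | 14.3.3.1 and 14.3.3.2 |
| ECG | 16.17.4 | yes | 14.3.4.1 to 14.3.4.4 |
| C-SSRS | 16.17.6 | not applicable | 14.3.5 |
| Weight, height, BMI | 16.17.5 | yes | none named |

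Two general statements do not fill the gap. Section 6.1 promises descriptive summaries where they are appropriate, but names neither these variables nor a table. Section 6.17 makes comparison with baseline the default for safety, and that is the comparison in which growth and drug effect are mixed. Section 6.17 also omits physical examinations from its list of safety components, although section 5.4 includes them.

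**2. What interval does the change cover?**

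Section 4 defines baseline as the last non-missing value before first dose. Weight is scheduled before dosing only at Screening, so Screening supplies the baseline. Visit 2 is Day 1 and Visit 10 is Day 56, which is 55 days later.

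- Longest scheduled interval: 28 + 55 = 83 days, or 11.9 weeks (85 days with the +2-day window).
- With Screening immediately before Visit 2: about 55 days, or 7.9 weeks.
- Early discontinuers have their end-of-study procedures at their last visit (section 3.3), and section 6.1 treats that visit as Visit 10, so their intervals are shorter.

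**3. How large could growth be? (assumption, not in the SAP)**

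If ordinary gain is 2 to 3 kg per year:

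- 2 × 8/52 = 0.31 kg
- 3 × 12/52 = 0.69 kg

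A shortfall of 0.5 kg falls within this range, so it could be listed as roughly no change.

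**4. How precise would a by-arm comparison be? (illustration)**

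The numbers per arm come from section 3.5. An effect size of 0.547 with 90% power at two-sided 0.05 gives 71.2, rounded up to 72 per arm (t-test power 0.903 at 72). Allowing for 27.9% non-completion, 72/(1 − 0.279) = 99.9, so 100 per arm and 300 in total. The plan's figures reproduce.

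The 95% CI half-width for a difference in mean change is 1.96 × SD × √(2/n). The SAP gives no SD for weight change, so the SDs are assumed:

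| Assumed SD (kg) | n = 72 per arm | n = 100 per arm |
|---|---|---|
| 0.8 | 0.26 | 0.22 |
| 1.0 | 0.33 | 0.28 |
| 1.2 | 0.39 | 0.33 |
| 1.5 | 0.49 | 0.42 |
| 2.0 | 0.65 | 0.55 |

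These figures are for weight only. No assumption is offered for height or BMI.

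**The case against.** The strongest reply is that nothing is lost. Weight and height are collected in all three randomized arms and the changes are already derived, so a by-arm table can be produced at any time. That is right. A reader might infer that the trial cannot separate growth from a drug effect. The documents do not support that, because the limitation lies in the planned outputs and not in the design or the data. The long screening interval does not bias a between-arm comparison either, since under randomization it affects all arms alike.

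A reader might also infer that a weight difference between arms would appear in no table at all. That is too strong. Weight or appetite changes reported as adverse events enter Table 14.3.1.2 by treatment group, and where applicable Tables 14.3.1.5 and 14.3.1.6. These tables depend on what is reported, however, and do not summarize measured change.

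The comparison with laboratory values, vital signs and ECG has a limit of its own. Those sections plan descriptive by-arm tables and, in places, shift or frequency tables. None plans a placebo difference with a confidence interval. Consistency alone therefore supports only a descriptive table. The case for a placebo difference rests on growth, and it is a preference rather than a correction.

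Finally, this is one table over an eight-week treatment phase, and efficacy is untouched. That limits the weight of the point but does not answer it.

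**Conclusion.** The point holds as a gap in planned safety reporting. Section 16.17.5 chooses a listing as the only output for change in weight, height and BMI, and no other section supplies a by-arm summary. In children aged 6 to 11, this leaves measured change without the placebo reference needed to interpret it. The primary and key secondary analyses, the sample size and the type I error rate are unaffected.

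The conclusion rests on the text and on children of this age growing over 8 to 12 weeks. It does not depend on the illustrative figures. Those figures indicate that a difference from placebo in weight change would have a 95% CI half-width of about 0.2 to 0.65 kg, for assumed SDs of 0.8 to 2.0 kg and 72 to 100 children per arm. A reader might infer that the added table would reliably detect a half-kilogram effect. The documents do not support that: they give no SD, and at the upper end of the assumed range the half-width exceeds 0.5 kg. Nor do they give any basis for a fixed percentage weight-loss threshold, which could also miss a shortfall offset by growth.

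**What to change.** In section 16.17.5, keep Listing 16.2.11.2 and add one table for the safety population. For weight, height and BMI it should give baseline, end-of-study value and change from baseline by treatment group (n, mean, SD, median, minimum, maximum). Preferably it should also give, for each dose, the difference from placebo in mean change with a 95% CI, labelled as descriptive and outside the multiplicity procedure. A footnote should state that baseline is the Screening value.

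The cost is one more table shell and its programming. The data are already collected and the changes already derived, so no protocol change or added procedure is needed.
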